13.2 Accrual Rate and Study Duration

With two sites participating and an anticipated accrual rate of 4-5 patients per month, we expect to enroll 45 patients in approximately 1 to 1.5 years. With an additional 6 months of follow-up, the total study duration is expected to be 2 years. If more than 9 patients (6 on combination arm, 3 on radium arm) have inadequate bone biopsy specimens to assess the primary endpoint, patients will be replaced.

Table	17:	Accrual	Targets
-------	-----	---------	---------

Accrual Targets						
Ethnic Category	Sex/Gender					
	Females		Males		Total	
Hispanic or Latino	0	+	8	=	8	
Not Hispanic or Latino	0	+	37	=	37	
Ethnic Category: Total of all subjects	0	+	45	=	45	
Racial Category						
American Indian or Alaskan Native	0	+	0	=	0	
Asian	0	+	8	=	8	
Black or African American	0	+	3	=	3	
Native Hawaiian or other Pacific Islander	· 0	+	1	=	1	
White	0	+	33	=	33	
Racial Category: Total of all subjects	0	+	45	=	45	

13.3 Stratification Factors

Patients will be stratified based on:

- Baseline alkaline phosphatase <220 or ≥ 220
- Volume of bone metastases (high: ≥ 4 bone metastases including one beyond the axial skeleton vs. low: <4 bone metastases)
 Based on CHAARTED (ECOG 3805) criteria²⁴

13.4 Sample size justification

The study plans to enroll 45 patients to ensure 36 patients to include in the primary analysis after taking into consideration that 20% patients may be lost to follow-up or have inadequate serum and tissue specimens for analysis.

The sample size justification is based on comparisons between the treatment arms of the increase in CD4+ T or CD8+T cell infiltration levels measured in the bone biopsy specimen from baseline to 8 weeks. Our primary biological hypothesis is that patients receiving pembrolizumab plus radium-223 will have a higher increase in CD8+ and CD4+ T cell infiltration from baseline to 8 weeks on treatment than patients treated with radium-223 alone. While little is known of CD8+ T cell levels in metastatic prostate cancer specimens, a 50% to 80% difference between the treatment arms for the increase in CD4+ or CD8+ T cells would represent a biologically meaningful treatment effect. With a total of 36 patients with adequate tissue/specimens for analysis, the study would provide 24 patients treated with the combination and 12 patients treated with radium-223 monotherapy. There would be 91% statistical power to detect a difference of increase in CD4/8 cell infiltration levels

between the treatment arms that is 1.2 times the population standard deviation (i.e. an effect size of 1.2, defined as the difference as a fraction of population standard deviation) using Wilcoxon rank sum test with two-sided type I error α =0.05. This corresponds to a hypothesis test for a 70% difference between the two treatment arms of the increase in CD4/8 T cell infiltration levels, with a population standard deviation (SD) of 58%. The following table provides statistical power to be achieved from a few other scenarios with effect size assumptions.

	Table 18: Statistical power for Wilcoxon rank sum test								
	Effect size								
	(Diffe	(Difference of the increase in CD4/8+ cell infiltration levels							
			between arms/	(SD)					
Evaluable		1.2							
Sample sizes	0.8	0.9	1	1.1	(=.7/0.58)				
100% enrolled									
N1=30, N2=15	69	79	86	92	96				
80% enrolled									
N1=24, N2=12	59	69	78	85	91				

13.5 Safety Monitoring Plan

Give there is no safety data for the combination therapy of pembrolizumab and radium-223, an early safety monitoring will be conducted to ensure that the combination therapy is well tolerated. A rate of targeted grade 3-5 AEs, particularly related to induction of immune phenomenon such as pneumonitis, colitis, and severe rash, in excess of 33% with combination therapy would be of concern. The safety assessments will be implemented after 15 (~50%) of the planned 30 subjects in the combination therapy arm have completed 12 weeks of combination therapy (including those who discontinued treatment because of toxicity), a focused safety review will be conducted. An estimated targeted AE rate with a one-sided binomial 90% CI will be constructed. If 5 or more of the first 15 subjects experience the targeted AEs (an observed 33% AEs rate, to have a upper bound of the CI <=53%), then the enrollment of combination therapy arm may be suspended pending the study team and DSMC review. The following table gives the operating characteristics of the early safety stopping; if the true unknown probability of grade \geq 3 AEs rate is 40% or higher, the probability of observing 5 or more subjects with grade \geq 3 AEs will be greater than 78.3% at the time of AE assessment.

Table 19: Operating characteristics of early safety monitoring

True/unknown G3+	Probability (%) of observing 5 or more \geq grade 3 AEs
AE rate (%)	in 15 subjects
20	16.4
30	48.5
40	78.3
50	94.1
60	99.1

The trial will be reviewed semi-annually by the DF/HCC Data and Safety Monitoring Board.

In addition to summarizing all AEs according to type and grade, all grade 4 (or higher) AEs will be listed for review.

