The following are considered events that should be reported to the Sponsor-Investigator within 24 hours of the site responsible investigator becoming aware of the event. The treatments are recommendations and the agents utilized should be determined by the treating clinician as deemed medically necessary.

Pneumonitis

The following AE terms, if considered \geq Grade 2, should be reported to the Sponsor-Investigator within 24 hours of the event:

- Pneumonitis
- Interstitial lung disease
- Acute interstitial pneumonitis

If symptoms indicate possible new or worsening cardiac abnormalities additional testing and/or a cardiology consultation should be considered. All attempts should be made to rule out other causes such as metastatic disease, bacterial or viral infection. It is **important that patients with a suspected diagnosis of pneumonitis be managed as per the guidance below until treatment-related pneumonitis is excluded. Treatment of both a potential infectious etiology and pneumonitis in parallel may be warranted. Management of the treatment of suspected pneumonitis with steroid treatment should not be delayed for a therapeutic trial of antibiotics.** If an alternative diagnosis is established, the patient does not require management as below; however, the AE should be reported to the Sponsor-Investigator regardless of etiology.

Course of Action

Grade 2 events:

- Report to Sponsor-Investigator
- Hold pembrolizumab.
- Consider pulmonary consultation with bronchoscopy and biopsy/BAL.
- Consider ID consult
- Conduct an in person evaluation approximately weekly
- Consider frequent Chest X-ray as part of monitoring

- Treat with systemic corticosteroids at a dose of 1 to 2 mg/kg/day prednisone or equivalent. When symptoms improve to Grade 1 or less, steroid taper should be started and continued over no less than 4 weeks.

- Permanently discontinue for inability to reduce corticosteroid dose to 10 mg or less of prednisone or equivalent per day within 12 weeks.

– Second episode of pneumonitis – discontinue pembrolizumab if upon re-challenge the patient develops a second episode of Grade 2 or higher pneumonitis.

Grade 3 and 4 events:

- Report to Sponsor-Investigator
- Discontinue pembrolizumab.
- Hospitalize patient
- Bronchoscopy with biopsy and/or BAL is recommended.

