Collect past medical history relevant to the event. Any preexisting conditions not previously reported (e.g., drug allergy) should be entered into the Medical History eCRF.

C. Presentation of the Event:

Collect information on clinical presentation and potential contributing factors. This information should be summarized and entered in narrative format in the AE eCRF. Please use the available free-text fields, such as Signs and Symptoms. Note pertinent negatives where applicable to reflect that the information was collected. Any treatments administered should be entered on the Concomitant Medication eCRF.

D. Vitals Signs and Standard Laboratory Tests:

Measure vital signs (pulse, sitting BP, oral temperature, and respiratory rate) and record on the Vital Signs eCRF. Perform standard laboratory tests (CBC with manual differential and serum chemistry panel, including LFTs).

E. Focused Skin Examination:

Perform a focused skin examination. Information should be summarized and entered on the Adverse Experience eCRF as part of the narrative.

F. Dermatology Consult

Refer the subject to a dermatologist as soon as possible.

- For a "severe rash", the subject must be seen within 1-2 days of reporting the event.

- For clinically significant rash, the subject should be seen within 3-5 days.

The dermatologist should submit a biopsy sample to a certified dermatopathology laboratory or to a pathologist experienced in reviewing skin specimens. The site should provide the dermatologist with all relevant case history, including copies of clinical photographs and laboratory test results.

Other/Miscellaneous Immune Related Toxicities

The following AEs, regardless of grade, should be reported to the Sponsor-Investigator within 24 hours of the event:

- Myocarditis
- Pericarditis
- Pancreatitis

– Any additional Grade 3 or higher event, which the physician considers to be immune related

All attempts should be made to rule out other causes. Therapeutic specialists should be consulted as appropriate. However, the AE should be reported to the Sponsor-Investigator regardless of etiology.

Course of Action

Grade 2 events or Grade 1 events that do not improve with symptomatic treatment:

- Withhold pembrolizumab.
- Systemic corticosteroids may be indicated.
- Consider biopsy for confirmation of diagnosis.
- If pembrolizumab held and corticosteroid required, manage as per grade 3 below.

Grade 3 events:

Hold pembrolizumab

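### Cheap improvement to 13.5: let the existing 5-of-15 combination-safety boundary act when the fifth case is confirmed, not only after the 15th Arm A patient completes 12 weeks

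*Combined protocol and SAP*

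**What the plan says.** Section 13.5 acknowledges that the two drugs have no safety record together and treats a targeted grade 3-5 AE rate above 33% as a concern. The targeted events are described by example, "particularly related to induction of immune phenomenon such as pneumonitis, colitis, and severe rash". A focused review takes place "after 15 (~50%) of the planned 30 subjects in the combination therapy arm have completed 12 weeks of combination therapy", counting patients who stopped for toxicity. The rule reads "If 5 or more of the first 15 subjects experience the targeted AEs", and its consequence is "then the enrollment of combination therapy arm may be suspended pending the study team and DSMC review". Table 19 gives the probability of crossing, but its column label and the sentence before it speak of grade 3 or higher AEs without the word targeted.

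No section holds or slows accrual while the first 15 are followed, and there is no second numerical look. On speed of enrolment, 13.2 states an "anticipated accrual rate of 4-5 patients per month, we expect to enroll 45 patients in approximately 1 to 1.5 years".

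Other oversight exists. Section 6.1 lists "events that should be reported to the Sponsor-Investigator within 24 hours of the site responsible investigator becoming aware of the event", covering pneumonitis, colitis, rash and, more generally, "Any additional Grade 3 or higher event, which the physician considers to be immune related". Section 7.3 sets 24 hours for SAEs, 12.2 provides DSMB review of toxicity twice a year, and 5.7 allows early termination on the incidence or severity of adverse reactions. None of these carries a number.

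**The concern.** The 50% in 13.5 describes how many Arm A patients are assessed, not how many will have been enrolled by then. Because enrolment continues through the 12 weeks of follow-up, the arm will be well past half full when the rule is first applied.

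The boundary could also be reached and have no effect for a time. If five of the first 15 are affected before the 15th patient reaches week 12, 13.5 prompts nothing until the review. Any earlier pause would rest on judgement without a threshold, for a combination whose toxicity 13.5 says is unknown.

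**Working it through.** **The plan's own figures.** With X ~ Binomial(15, p), P(X ≥ 5) at p = 20, 30, 40, 50 and 60% is 16.4, 48.5, 78.3, 94.1 and 99.1%, as in Table 19. The one-sided 90% Clopper-Pearson upper bound for 5/15 is 53.2%, against 53% stated. The rule is correctly calculated.

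**Arm A enrolment at the review.** Inputs: 2:1 allocation and 30 Arm A patients (13.1, 13.5); 4-5 patients per month (13.2); and 2.5-3.75 per month, which is 45/18 to 45/12 from the 1 to 1.5 years also in 13.2. Twelve weeks is 84/30.44 = 2.76 months. With steady accrual at r per month:

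- 15th Arm A patient enrolled at 15/(2r/3) = 22.5/r months
- review at 22.5/r + 2.76 months
- Arm A enrolled at review = 15 + (2r/3) × 2.76

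| r per month | 15th enrolled (month) | Review (month) | Arm A enrolled | % of 30 |
|---|---|---|---|---|
| 2.5 | 9.0 | 11.8 | 19.6 | 65 |
| 3.75 | 6.0 | 8.8 | 21.9 | 73 |
| 4 | 5.6 | 8.4 | 22.4 | 75 |
| 5 | 4.5 | 7.3 | 24.2 | 81 |

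That is 4.6-9.2 patients beyond the 15. These are means. With Poisson accrual the 5th-95th percentiles are about 16-23 at 2.5 per month and 20-29 at 5 per month.

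**Why earlier action leaves Table 19 alone.** A confirmed count among the same 15 patients can only rise. Reaching five early is therefore the same event as having five at week 12, provided the same confirmed events are counted both times. If unconfirmed reports were counted and 10% or 20% were later reclassified (assumed), the apparent rate at a true 20% would be 0.20/0.9 = 22.2% or 0.20/0.8 = 25%, and crossing would rise from 16.4% to about 23% or 31%.

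**Size of the benefit.** Simulation: 40,000 trials per cell, Poisson Arm A accrual, and enrolment stopping at the fifth affected patient plus any confirmation lag, capped at the planned review. Events fall uniformly over 12 weeks or within weeks 6-12 (both assumed; the documents give no timing for this combination). Mean Arm A patients spared over all trials, across the four rates:

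| True rate | Lag | Uniform | Weeks 6-12 |
|---|---|---|---|
| 40% | none | 5.1-6.6 | 4.3-5.1 |
| 40% | half month | 4.5-5.4 | 3.6-3.8 |
| 30% | none | 2.6-3.6 | 2.2-2.6 |
| 30% | half month | 2.3-2.8 | 1.7-1.8 |

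At a true 20% the saving is 0.6-1.0 without the lag and 0.5-0.8 with it.

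These runs assume that nobody acts before the review and that every crossing leads to suspension. If instead the DSMB met at months 6 and 12 from first enrolment and paused Arm A whenever five of the first 15 were already affected (assumed), the saving with the lag falls to about 2.0-3.1 at a true 40% and 1.0-1.6 at 30%.

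**The case against.** The timing is stated openly, the operating characteristics are right and suspension is discretionary, so this can be seen as a preference for a running count over one look. That stands as to category: nothing here is a mistake.

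Existing oversight could well act first. The trial is open label, the named immune events and SAEs reach the Sponsor within 24 hours, and with a review at month 7.3-11.8 a twice-yearly DSMB meeting would normally come earlier. This also stands, and it is why the savings are upper bounds. A reader might infer that the combination goes unmonitored until the review; 5.7, 6.1, 7.3 and 12.2 show otherwise. What they lack is a numerical trigger.

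Event timing is uncertain. Section 7.1.1.1 says immune events can appear months after the last dose, and later events shrink the benefit. Counting toxicity discontinuations before week 12 could bring the review forward slightly (about 0.2-0.5 patient), while time for data cleaning, not modelled here, would push enrolment the other way.

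An early review may rest on incomplete follow-up, including at a true 30%, below the 33% concern level, where 48.5% of trials cross. That cost is real, but those trials cross under the present rule too; only the date of any pause moves.

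**Conclusion.** The point holds as a cheap improvement to a design choice. Section 13.5's only numerical combination rule is applied once, with no stated hold while the first 15 are followed, and mean Arm A enrolment is then about 20-24 of 30. This rests on steady accrual at the rates in 13.2.

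As upper bounds (no earlier action under existing oversight, suspension at every crossing, all events within 12 weeks), the mean saving is about 4-7 Arm A patients at a true 40% rate, about 4-5 with a half-month lag, about 2-4 at 30%, and about 1 or less at 20%. Under the assumed DSMB schedule the true-40% figure with the lag is about 2-3.

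Two stronger readings are not supported. Table 19 is not wrong. Nor can one say that the plan will expose a given number of patients needlessly, because the documents fix neither event timing nor what the study team or DSMB would do sooner.

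**What to change.** Amend 13.5 as follows:

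- The boundary counts as met once a targeted grade 3-5 AE has been confirmed in the fifth of the first 15 Arm A patients. The consequence stays the discretionary suspension and review that 13.5 already provides.
- The 12-week assessment and confidence interval on the 15 patients are completed whether or not the boundary is met early.
- One definition of the targeted AE, set by the sponsor as a closed list, serves the running count, the 12-week review, and the label and sentence of Table 19. The table's probabilities then stay as they are.

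The cost is protocol wording, a running count and a confirmation step, with no extra patients. Confirmation is needed because 6.1 requires reports whatever the cause; for pneumonitis with another diagnosis established, "however, the AE should be reported to the Sponsor-Investigator regardless of etiology". Any listed AE outside the 24-hour sets reaches the study only through the routine case report forms of 7.7 and would need faster reporting. The downside is that a review may rest on incomplete 12-week follow-up, and any pause may come earlier in the 16.4% (true 20%) or 48.5% (true 30%) of trials that cross anyway.

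Separate minor point: in 13.2, 45 patients at 4-5 per month takes 45/5 = 9 to 45/4 = 11.25 months, not 12-18. The two statements should be reconciled; the conclusion above holds under either.

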13.6 Definition of Analysis Populations

Safety population: All patients who have received at least one dose of radium-223 or pembrolizumab will be included in safety assessment.

Primary analysis population: All patients who receive at least one dose of radium-223 and if in arm A, one dose of pembrolizumab and have bone biopsy assessment at baseline and 8 weeks will be included to assess primary, secondary, and exploratory endpoints.

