9.1.1 Bone biopsies

The bone biopsies will be core needle or excisional biopsies. These biopsies will be performed per standardized clinical guidelines at Brigham and Women's Hospital and at the corresponding department for participating investigational sites. Tissue will be embedded into paraffin. Sites that have been previously irradiated are not permitted. The second biopsy should be done at the same site as the original biopsy when possible. If the first biopsy is non-diagnostic, a second pre-treatment biopsy should be performed if safe and acceptable to the patient and treating physician. The patient will not be eligible to enroll if no tumor tissue can be identified by the pathology team (touch prep evaluation will suffice). If the patient is enrolled and it is later determined that the first biopsy is not diagnostic or useful towards assessing the primary endpoint of increase in T cell infiltrate, then they will not be required to undergo the on-treatment biopsy. If the patient

is already on study treatment, they may continue on the study therapy even if no ontreatment biopsy is obtained.

The on-treatment biopsy should be done after at least 2 doses of radium-223 unless the second dose of radium-223 cannot be given due to safety/toxicity. If the latter, it should follow the protocol dictated time window (week 8 or within 3 weeks after week 8). If it cannot be performed for safety reasons or patient refusal (as long as patient initially agreed), it will not be considered a deviation.

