L: Diagnostic CT chest and CT or MRI of the abdomen and pelvis and bone scan including SPECT/CT should be obtained at baseline and every 12 weeks (+/- 7 days). (NOTE: SPECT/CT will be done only at DFCI.) Scans should remain on an every 12 week schedule (+/- 7 days) even if dose delays occur.

M*: Correlative immune studies: will be obtained and transported overnight at room temperature to the [name] Lab at UCSF. Samples for immune studies will be done at week 1 (pre-dose), week 5, week 9, week 13, week 21 and at the time of progression for those patients still on study.

N: Bone biopsy: archival tissue is permitted for baseline analysis. IR guided bone biopsy will be done at week 8 (+3 weeks) after the second dose of radium-223. If the second dose cannot be given for safety reasons, biopsy should still be performed within the window detailed here.

O: Blood samples for cell free DNA (cf-DNA) will be performed at treatment initiation (week 1, pre-dose), on treatment (week 5 and 13), and at time of progression.

P: Quality of life, pain and analgesic use will be measured via the FACT-P (Appendix B), Brief Pain Inventory (Short Form) (Appendix C), and analgesic diary (Appendix D) prior to treatment, at week 5, 9, then every 6-8 weeks after week 9 (as schedules differ between the two arms), and at treatment progression/off study visit.

Q: After progression/treatment discontinuation, follow the participant for survival, receipt of next line therapies, and post-treatment SSEs every 6 months until death or 2 years after treatment discontinuation.

R: Arm A study assessments will continue based on the same schedule as detailed for weeks 1-13 when pembrolizumab is given alone (e.g., visits, labs, assessments every 3 weeks only). If radium-223 is resumed upon progression, assessment schedule and radium-223 + pembrolizumab dosing will resume based on the schedule detailed for weeks 1-13. Arm B study assessments and radium-223 dosing will continue based on the same schedule detailed for weeks 1-13 up to 6 doses without breaks except for toxicity/intolerance (Section 6.2).

Note: For both arms: Immune studies will follow the schedule detailed in footnote M*

S: End of Treatment visit should occur within 30 days after last study treatment.

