11. MEASUREMENT OF EFFECT

11.1 Antitumor Effect – Solid Tumors

For the purposes of this study, participants should be re-evaluated for response every 12 weeks (\pm 7 days). In addition to a baseline scan, confirmatory scans should also be obtained 12 (not less than 6) weeks following initial documentation of progressive disease.

Response and progression will be evaluated in this study using the new international criteria proposed by the Response Evaluation Criteria in Solid Tumors (RECIST) guideline (version $1.1)^{52}$ and PCWG2²³.

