13.8 Analysis of Secondary Endpoints

Safety and Tolerability: All adverse events recorded during the trial will be summarized for the safety population. The incidence of events that is new or worsening from the time of first dose of treatment will be summarized according to system organ class term, severity (based on CTCAE version 4.0 grade), type of adverse event, and relation to study treatment. For the combination therapy, special interests include toxicities related to induction of immune phenomenon such as pneumonitis, colitis, and severe rash. The frequency of AEs will be summarized separately according to treatment arms, with 90% exact binomial confidence intervals (CI). The proportion of patients in each arm with grade 4 or higher AEs will also be reported with an exact binomial 90% CI.

Deaths reportable as SAEs and non-fatal serious adverse events will be listed by patient and tabulated by primary system organ class, and type of adverse event.

PFS and OS: The distributions of time to PSA progression, PFS and OS will each be summarized using the product-limit method of Kaplan-Meier according to treatment arms. Median times for each endpoint will be presented with two-sided 95% confidence intervals estimated using log(-log(survival)) methodology. Kaplan-Meier estimates of the endpoints at 6 or 12 months after treatment initiation may also be presented with two-sided 95% confidence intervals.

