13.12.2 Evaluation of the Primary Efficacy Endpoint

There is no primary efficacy endpoint.

Analyses of secondary efficacy endpoints will be on an intent-to-treat basis. Specifically, all eligible participants included in the study must be assessed for response/outcome to therapy, even if there are major protocol therapy deviations.

Subanalyses may then be performed on the basis of a subset of participants,

excluding those for whom major protocol deviations have been identified (e.g., early death due to other reasons, early discontinuation of treatment, major protocol violations, etc.). However, these subanalyses may not serve as the basis for drawing conclusions concerning treatment efficacy, and the reasons for excluding participants from the analysis should be clearly reported. If applicable to the endpoint, the 95% confidence intervals will be provided.

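### Sections 13.6 and 13.12.2 name different analysis sets for PFS and OS with no order of precedence; following 13.6 would tend to overstate both

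*Combined protocol and SAP*

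**What the plan says.** Section 13.6 defines two sets. The safety population is everyone who received a dose. The primary analysis population is treated patients (in Arm A, with at least one dose of each agent) who "have bone biopsy assessment at baseline and 8 weeks will be included to assess primary, secondary, and exploratory endpoints".

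Section 13.12.2 states: "Analyses of secondary efficacy endpoints will be on an intent-to-treat basis". It explains this as assessing all eligible participants even after major therapy deviations. It allows subset analyses that drop, for example, early deaths or early discontinuations, but adds that "these subanalyses may not serve as the basis for drawing conclusions concerning treatment efficacy".

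PFS and OS are the secondary efficacy endpoints (1.3, 13.1). Section 13.8 plans Kaplan-Meier curves and medians by arm, and "Kaplan-Meier estimates of the endpoints at 6 or 12 months after treatment initiation may also be presented". It names the safety population for adverse events and no population for PFS or OS.

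On timing, the study calendar (note N) says "IR guided bone biopsy will be done at week 8 (+3 weeks) after the second dose of radium-223". Section 9.1.1 accepts a missed on-treatment biopsy without calling it a deviation: "If it cannot be performed for safety reasons or patient refusal". It also lets a patient already on treatment continue without one. PFS starts at first dose in 13.1 but at randomization (or registration) in 11.1.8; OS starts at randomization (or registration).

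**The concern.** The two rules cannot both hold for PFS and OS. One keeps every eligible participant. The other admits a patient only after something that happens about two months into follow-up.

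If 13.6 is followed as written, a patient who dies before the biopsy can never enter the set, and one who deteriorates may be too unwell for the procedure or may refuse it. Time still counts from first dose or randomization, so everyone in the set carries a stretch of guaranteed survival. The Kaplan-Meier medians and the 6- and 12-month estimates by arm then tend upward.

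These estimates are the trial's preliminary efficacy evidence, in an open-label study. With no stated precedence, the set could also be chosen after the data are seen.

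**Working it through.** **How far apart the sets are.** Section 13.4 enrols 45 to obtain 36, allowing that "20% patients may be lost to follow-up or have inadequate serum and tissue specimens for analysis". This reproduces: 36 / (1 − 0.20) = 45. On the plan's own loss rate the sets differ by 45 − 36 = 9 patients. The split between outcome-related and technical losses is not given. Section 13.2 replaces patients when more than 9 have inadequate specimens, so 9 is not a ceiling.

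**Inputs for an illustration**
- Biopsy time: week 8 = 8 × 12 / 52.18 = 1.84 months; week 11 = 2.53 months.
- OS: the 14.9-month radium-223 median cited in 2.2.1. Because this trial requires ECOG 0–1 and excludes visceral disease, 20 and 25 months are added as assumptions.
- PFS: the 13.11 inputs, namely medians of 6 months without and 12 months with a DDR mutation, at 30% prevalence.
- Assumptions: constant hazard within each group; only deaths before week 8 are excluded; all other missed biopsies are unrelated to outcome.

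**OS.** The fraction dying before time w is d = 1 − exp(−ln2 × w / m). The retained patients have median m + w and 12-month survival S(12) / (1 − d).
- m = 14.9: d = 0.082, and 45 × 0.082 = 3.7 patients. The median becomes 14.9 + 1.84 = 16.7 months. S(12) goes from 0.572 to 0.572 / 0.918 = 0.623.
- If every biopsy were at week 11, the median would be 14.9 + 2.53 = 17.4 months.

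**PFS.** S(t) = 0.7 exp(−ln2 × t/6) + 0.3 exp(−ln2 × t/12).
- Setting S(t) = 0.5 gives a median of 7.26 months.
- With a fraction d excluded, the median solves S(t) = 0.5 (1 − d).
- S(6) = 0.7 × 0.5 + 0.3 × 0.7071 = 0.562; with d = 0.082 it becomes 0.562 / 0.918 = 0.612.

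| OS median assumed | Deaths before week 8 | OS median under 13.6 | Rise | PFS median under 13.6 | Rise |
|---|---|---|---|---|---|
| 14.9 | 8.2% | 16.7 | 12.3% | 8.18 | 12.8% |
| 20 | 6.2% | 21.8 | 9.2% | 7.95 | 9.5% |
| 25 | 5.0% | 26.8 | 7.4% | 7.81 | 7.6% |

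The two endpoints move by nearly the same proportion. At 14.9 months the rate shifts also match: +5.1 points for 12-month OS and +5.0 points for 6-month PFS.

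**Scale.** With all 30 Arm A patients followed to death, an exponential 95% interval around 14.9 months runs from 14.9 × 60 / χ²(0.975; 60) to 14.9 × 60 / χ²(0.025; 60), which is 10.7 to 22.1 months. A shift to 16.7 lies well inside it.

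**The case against.** The best defence is that 13.12.2 is the specific rule and 13.6 a loose general sentence. Section 13.12.2 says all eligible participants must be assessed, and it bars efficacy conclusions from subsets that drop early deaths. Other sections already depart from 13.6: safety, also a secondary endpoint, has its own population, and 13.11 plans a PFS analysis on at least 40 patients, more than the 36 expected to be evaluable. This makes intent-to-treat the likelier intention. It does not settle the matter: 13.6 is the section that defines the populations, it names secondary endpoints outright, and no text ranks the two.

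It is also fair that the size is hypothetical. It borrows a median from another trial and assumes constant hazard from the first day. If all 9 expected losses were technical and unrelated to outcome, there would be no bias.

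A reader might infer that the problem is confined mainly to OS, because "participants should be re-evaluated for response every 12 weeks" puts the first scheduled scan after the biopsy window. The late scan does mean that few progressions can be recorded before the biopsy. But deaths are PFS events too, and excluding them alone moves both endpoints by similar proportions. The PFS shift is smaller only in months, because its median is shorter.

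A reader might also infer a biased treatment comparison. The documents do not support that: 13.8 plans no between-arm test of PFS or OS, and nothing shows that early losses would differ by arm.

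**Conclusion.** The contradiction is certain and should be fixed; its numerical effect is conditional. If 13.12.2 governs, this bias does not arise. If 13.6 is followed, absolute PFS and OS tend to be too high whenever early death or deterioration causes missed biopsies. Under the stated assumptions, with OS medians of 14.9 to 25 months, the rise is about 7 to 13% for both medians. The documents fix neither the share of losses related to outcome nor the true medians, so these figures are an illustration and not a prediction. It would go too far to say that the reported PFS and OS will be inflated, since that depends on which rule the team applies. The 36-patient primary comparison and its stated 91% power are untouched.

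**What to change.** - In 13.6, limit the paired-biopsy set to endpoints measured on paired biopsies.
- In 13.6 and 13.8, state that PFS and OS use the 13.12.2 intent-to-treat set, by assigned arm.
- Choose one PFS time origin consistent with that set, since 13.1 and 11.1.8 now differ. Say how patients who are randomized but never treated are handled, because 4.1 cancels their registration and they have no first dose.
- Assign the exploratory endpoints that need no paired biopsy (PSA, SSE, quality of life, blood-based and genomic) to all patients with the relevant data. Otherwise narrowing 13.6 leaves them without a population.
- Label any PFS or OS analysis in biopsy-evaluable patients as supportive only, as 13.12.2 already requires of subsets.

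The cost is wording, best settled before PFS and OS are analysed. Reported medians may be slightly less favourable. Some early drop-outs will be censored early for PFS, because 5.5 does not require follow-up scans in patients who stop without progression.
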